### 3.9 Total Study Duration and Duration of Treatment

████████████████████ The treatment duration of each study drug arm may vary depending on the enrollment rate, the respective sample size, and the treatment time needed for the study drug to achieve its goal. A study drug arm may be stopped early or revised (e.g., dose adjustment or treatment duration), based upon the results of the interim analyses or information from other clinical trials for the same drug, as outlined in each drug-specific appendix.

For the gantenerumab and solanezumab arms, subjects will continue to receive blinded treatment until **every subject** randomized to either the gantenerumab or solanezumab blinded study drug arms has received a minimum of 4 years (208 weeks) of treatment or is withdrawn. Based on the time that was needed for full recruitment, the total duration of the gantenerumab and solanezumab arms is expected not to exceed 81 months (6.75 years), which allows 33 months for enrollment and 48 months for treatment. For subjects enrolled in the first month,

the duration of treatment will be approximately 80 months (32+48); for those enrolled in the last month, the duration of treatment will be 48 months; and for those enrolled in-between, the duration of treatment will be approximately from 48 months to 80 months. On average, the duration of treatment per subject is about 64 months (5.3 years).

The sponsor may choose at any time to limit treatment duration to 4 years (208 weeks) for a study drug arm even if some subjects have exceeded this limit at the time of the decision.

[REDACTED]

After the final analysis is complete for a study drug arm, subjects may be eligible to continue or start treatment in the open-label extension period (section 3.10) if the study drug arm demonstrates clinical or cognitive benefit.

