### **4.4 Discontinuation/Early Withdrawal of Subjects**

#### **4.4.1 Criteria for Discontinuation**

Subjects could be discontinued from the double-blind period or OLE for any of the following reasons:

1. Subjects would be discontinued from this study if they were involved in any other clinical trial or other research judged not to be scientifically or medically compatible with this study. Participation in any other concurrent clinical trial that studies an investigational drug or any procedures to improve cognition is not permitted.
2. Site principal investigator, Medical Director, PAL, or Medical Monitor decides subject should be discontinued, e.g., after an SAE or other clinically significant event or laboratory finding. See each drug-specific appendix for any drug-specific discontinuation criteria related to adverse events and laboratory findings.

Decisions regarding subjects who have ARIA AEs will be made based on both imaging and clinical factors; decisions will be made by the Medical Director following discussion between site principal investigator or designated sub-investigator, Medical Director and/or designee, and Project Arm Leader using drug-specific guidelines in Appendices 3 and 4.

3. Subject or subject research proxy (if subject is cognitively impaired and unable to provide their own consent) decides to withdraw consent, including declining to consent to any protocol amendments.
4. Subject becomes pregnant.
5. Subject non-compliance, based on decision of site study staff or Medical Monitor. For parenteral drugs administered every 4 weeks, this includes subjects who fall below 75% compliance with respect to dosing, e.g., those who miss more than 7 study drug doses during the four-year study or who miss more than 3 consecutive doses of study drug. For daily oral administration, subject non-compliance is to be determined by the principal investigator in collaboration with the study medical staff after review of the subject's study drugs usage. Determination of non-compliance would not apply to doses that are missed or reduced when the site principal investigator and Medical Director decide that changes in study drug dosing are necessary for medical or safety reasons.

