#### **5.4 Treatment Compliance**

Compliance will be monitored for all drugs and recorded on study documents. See each drug-specific appendix for specific compliance monitoring for each study drug.

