## 1.13 Drug-specific Safety Concerns

### 1.13.1 Amyloid related imaging abnormalities (ARIA)

As outlined above (section 1.4), ARIAs are a special safety endpoint in studies of Alzheimer's immunotherapies, including both active and passive immunization. This study includes frequent MRI scans to assess for ARIA changes. ARIA can occur as either cerebral edema/effusion (ARIA-E) or as hemorrhages (ARIA-H), typically microhemorrhages, but possibly larger hemorrhages or infarction (Sperling et al., 2012).

Time points for Safety MRI at the 225 mg dose level were originally scheduled for: before the first dose (baseline scan for safety reads done at V2) and then about 1 week after dose 2; dose 4; dose 6; dose 9; dose 17 and dose 22. Additional safety MRIs were scheduled as part of the volumetric MRI at the annual assessments before dose 14 (V15, week 52), dose 27 (V28, week 104), dose 40 (V41, week 156), and V54 (week 208).

Following the approval of Amendment 5, all subjects will sign the new ICF and initiate up titration starting at the 450 mg dose level. Subjects may be at different time points in the schedule of visits when initiating titration, therefore safety MRIs will be scheduled based on the DIAN-TU-001 Gantenerumab Titration Safety MRI Schedule (Table 5). A safety MRI will be scheduled 1 week after the second dose of each titration step, unless otherwise indicated by the ARIA-E and ARIA-H management algorithms (section 1.15). If an annual visit follows the second dose of a titration step, the annual MRI assessment can fulfill this requirement as long as the MRI reading is reviewed prior to dosing at that visit. Although the titration schema was designed to reach the target dose of 1200 mg administered every 4 weeks, the target dose may not be achieved as otherwise dictated by the ARIA-related intervention algorithms or more conservative action by the site/sponsor. The stable dose is defined as the maximum dose the subject will remain at for the duration of the trial based on safety. Once a subject reaches their stable dose, safety MRIs will be scheduled to follow every third dose (or approximately every 3 months). Additional safety MRIs are done as part of the volumetric MRI at the annual assessments: Visit 15 (week 52), Visit 28 (week 104), Visit 41 (week 156), Visit 54 (week 208), Visit 67 (week 260), Visit 80 (week 312), and Visit 93 (week 364).

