23. PET imaging studies may be omitted if early termination (ET) occurs less than 6 months after the previous PET imaging or if precluded by local regulations/dosimetry limits. Other procedures may also be eliminated on a case-by-case basis, as determined by the sponsor.

- . See section 1.12 for details of drug-specific samples at early termination (ET) visit.  
. Study drug administration only if subject is continuing double-blind treatment beyond year 4.

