### 2.2 Drug Treatment Regimen

This study was initiated as a comparison of solanezumab (400 mg administered as an intravenous infusion of approximately 70 mL) compared to placebo. The active drug group was given an intravenous infusion of solanezumab 400 mg Q4W.

The study protocol was amended to increase the dose administered up to 1600 mg Q4W; following approval of Amendment 7, the dose-escalation process will begin (which includes signing a new ICF). After receiving at least two doses at the 400 mg level, 4 weeks ( $\pm$  4 days) apart, subjects should receive at least two doses at the 800 mg dose level, 4 weeks ( $\pm$  4 days) apart, before proceeding to the 1600 mg dose level. Changes in dosage may be made in the event of ARIA as described in section 1.14 or for other safety reasons at the investigator's discretion with notification of a Medical Director, PAL, or designee.

In addition to the Solanezumab Schedule of Visits, additional assessments during the dose escalation period are required, as described in the dose escalation study schedule. The first doses of 800 mg will be given at the DIAN-TU site or a medically qualified facility, such as an infusion clinic, until blinded safety results are evaluated for the first 20 subjects (active or placebo) to receive an 800 mg dose infusion (Table 5); subsequent doses may be given by a home health nurse. After the safety evaluation, first doses of 800 mg for the remaining subjects may be given by a home health nurse, if deemed appropriate (Table 6).

Similarly, the first doses of 1600 mg will be given at the DIAN-TU site or a medically qualified facility such as an infusion clinic until blinded safety results are evaluated for the first 20 subjects (active or placebo) to receive a 1600 mg dose infusion (Table 5). After this evaluation, first doses of 1600 mg for the remaining subjects may be given by a home health nurse, if deemed appropriate (Table 6).

All subjects will have a 1-hour post dose monitoring period after their first 800 mg and first 1600 mg doses.

Subjects will continue dosing for up to a minimum of 204 weeks and a maximum of 360 weeks based upon when the subject was randomized into the study.

**Table 5** DIAN-TU-001 Solanezumab Schedule of Visits: Dose Escalation Period (At least 20 Subjects for Each Dose Level)

PROCEDURE:	Dose (mg)	800	800	sMRI	1600	1600	1600	1600
	VISIT SITE	DIAN-TU a	H	MRI	DIAN-TU a	H	H	H

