## **2.6 Assessing Compliance with Study Drug**

DIAN-TU site staff or trial-designated home health nurse should document completion of infusion on study source documents. Because dosing occurs at study visits, subjects who attend all visits and successfully receive infusions are automatically compliant with treatment. Any infusion at which 75% (approximately 52.5 mL for 400 mg doses, 180 mL for 800 mg doses, and 210 mL for 1600 mg doses) or more of the infusate is given will be considered a complete infusion.

If a subject attends a visit but does not receive a complete infusion (for example, due to technical complications), every effort should be made to reschedule the infusion within 24 hours if possible. If less than 75% of the infusate is given, this must be recorded as an incomplete infusion in the study source documents.

Missed infusions should be recorded on the study source documents. Subjects who miss 3 consecutive infusions or 7 overall may be discontinued from the study unless infusions are intentionally held due to ARIA or other AE.

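### Protocol Section 4.4.1 item 5: more than 7 missed doses in four years is not compliance below 75%; 8 missed of 52 is 84.6%, and below 75% starts at 14 missed

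*Protocol*

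**What the plan says.** Protocol Section 4.4.1 lists reasons for which a subject could be discontinued. Item 5 is non-compliance, as judged by site staff or the Medical Monitor. For parenteral drugs given every four weeks it includes "subjects who fall below 75% compliance with respect to dosing, e.g., those who miss more than 7 study drug doses during the four-year study", and the sentence continues "or who miss more than 3 consecutive doses of study drug". Doses missed or reduced because the site principal investigator and the Medical Director decide so for medical or safety reasons do not count.

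Section 5.4 refers onward: "See each drug-specific appendix for specific compliance monitoring for each study drug". The gantenerumab appendix (Appendix 3, Section 2.1.6) shows no limit on the number of missed doses. The solanezumab appendix (Appendix 4, Section 2.6) has its own wording, with no percentage: "Subjects who miss 3 consecutive infusions or 7 overall may be discontinued from the study", unless infusions are held for ARIA or another adverse event.

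**The concern.** Item 5 puts a percentage, a count, a dosing interval and a period into one sentence, and offers the count as an instance of the percentage. Over the stated period it is not an instance of it. Site staff and the Medical Monitor thus have two numbers for one judgement, and the numbers disagree over a band of missed-dose counts. In the gantenerumab arm this sentence is the only numerical limit on missed doses that the protocol shows, so nothing else settles the matter.

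At stake is consistency: whether a subject with, say, ten missed doses is treated as non-compliant could depend on which half of the sentence the site reads. The protocol regards retention as essential (Section 3.2) and does not replace subjects after the first dose (Section 4.4.2), so the wording deserves to be right even though the decision is discretionary.

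**Working it through.** **Inputs**
- Dosing interval: 4 weeks (Section 4.4.1 item 5).
- First dose: week 0, Visit 2.
- Last dose of the four-year period: week 204. For solanezumab, Appendix 4 Section 2.2 says "Subjects will continue dosing for up to a minimum of 204 weeks and a maximum of 360 weeks"; Appendix 3 Section 2.1.2 gives the same limits for gantenerumab.
- Week 208: footnote 25 of the gantenerumab four-year schedule says "Study drug administration only if subject is continuing double-blind treatment beyond year 4"; footnote 26 of the solanezumab schedule agrees.
- Threshold: below 75%. Count given as its example: more than 7 missed, that is, 8 or more.

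**Step 1: number of doses.** Weeks 0, 4, ..., 204 give 204/4 + 1 = 52 doses, with dose k at week 4(k − 1). Appendix 3 Section 1.13.1 numbers the doses the same way: "dose 14 (V15, week 52), dose 27 (V28, week 104), dose 40 (V41, week 156". The formula gives weeks 52, 104 and 156 for doses 14, 27 and 40, and week 204 for dose 52.

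**Step 2: does the plan's figure reproduce?** Compliance with m missed doses is (52 − m)/52. With m = 8 it is 44/52 = 84.6%, which is not below 75%. The figure does not reproduce.

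**Step 3: where below 75% starts.** (52 − m)/52 < 0.75 requires m > 13.

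| Missed of 52 | Compliance | More than 7 missed? | Below 75%? |
|---|---|---|---|
| 7 | 45/52 = 86.5% | no | no |
| 8 | 44/52 = 84.6% | yes | no |
| 13 | 39/52 = 75.0% | yes | no |
| 14 | 38/52 = 73.1% | yes | yes |

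The count and the percentage disagree for 8 to 13 missed doses.

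**Step 4: other denominators.**
- Counting week 208 as a 53rd dose: 8 missed is 45/53 = 84.9%, and below 75% still starts at 14 (39/53 = 73.6%; 13 missed is 40/53 = 75.5%).
- With 51 doses: 8 missed is 43/51 = 84.3%, and below 75% starts at 13 (38/51 = 74.5%).
- More than 7 is the exact 75% cut-off only if (n − 7)/n ≥ 0.75 and (n − 8)/n < 0.75, that is, n = 28 to 31. Doses 28 and 31 fall at weeks 108 and 120, a little over two years.

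No four-year denominator makes 8 missed doses fall below 75%.

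**The case against.** **The count is only an illustration.** An illustration still has to be an instance of what it illustrates, and this one is not. If the count was meant as a rule of its own, the 75% would never bind over four years, because the count is reached first. Both readings need an edit.

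**The percentage could refer to doses scheduled so far.** Over about 28 to 31 doses the two figures would agree, and a reader might infer that the count was set for a two-year period. The text does not say so; it ties the count to four years.

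**The practical effect is small.** This stands. The decision is discretionary and safety-related holds are exempt, which narrows the 8-to-13 band. Section 6.3.7 encourages continued assessments after dosing stops. The mITT set (Section 8.4.1) needs only randomisation, treatment and one cognitive assessment after baseline, so neither figure removes anyone from it. Section 6.3.5 also puts the end of double-blind visits at November 2019, and Appendix 3 Section 1.4 already cites a data cut-off of 31 May 2019, so few double-blind decisions may remain. Section 4.4.1 also covers the open-label extension.

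**Two stronger readings are tempting.** A reader might infer that the limit of more than 3 consecutive doses is a second arithmetic error, since it follows in the same sentence. The documents do not support that: the clause reads naturally as a separate trigger, it is tied to no period, and Appendix 4 Section 2.6 likewise lists consecutive and overall misses side by side without a percentage. A reader might also infer that the Appendix 4 limits contradict the main protocol. Sections 5 and 5.4 leave compliance detail to the drug appendices, so a slightly different solanezumab rule may be deliberate and is not an error.

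**Conclusion.** The point holds as a mismatch between two figures in one sentence. Over 52 four-weekly doses, more than 7 missed means compliance of 84.6% or less, whereas below 75% means 14 or more missed. The conflict is confined to subjects missing 8 to 13 doses for reasons other than a medical or safety decision. The protocol does not say which figure governs.

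This rests on one dose every four weeks from week 0 through week 204, which the visit schedules and the protocol's own dose numbering support, and on compliance being doses received divided by doses scheduled. Adding a week 208 dose changes neither the band nor the conclusion.

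A reader might infer that the mismatch threatens the primary analysis. It does not: sample size, type I error and the mITT set are unaffected. It is a threshold that should be corrected, with limited consequences if it is not.

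**What to change.** Make the percentage and the count in Section 4.4.1 item 5 agree, and name the 52 doses scheduled over four years as the denominator.

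- **Preferred:** keep more than 7 missed and restate the percentage as below about 86%. Then 7 missed (86.5%) is allowed and 8 missed (84.6%) is not. This keeps the main protocol close to the limit of 7 overall in Appendix 4 Section 2.6.
- **If 75% is the intended rule:** change the count to more than 13 of 52, and reconcile Appendix 4 Section 2.6 in the same amendment, because this choice would widen the gap with that section.

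In either case, word the limit of more than 3 consecutive missed doses as a separate trigger that applies whatever the overall percentage.

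The cost is one figure and a few words in Section 4.4.1, plus one sentence in Appendix 4 if the second option is taken. Design, sample size and analysis do not change.

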#### 4.4.2 Replacement of Subjects

Enrollment for each study drug arm will be ongoing until all groups within the study drug arm are filled. Subjects will be replaced only when they withdraw from the study before the first dose of study drug is dosed/administered.

#### **4.5 Transfer of Subjects Between Sites**

A subject may request a transfer to a different DIAN-TU site if they relocate or if transfer to a new site will enable improved compliance with all study visits and procedures. Should the trial be closed at a DIAN-TU site, subjects from the closing site would be offered the option of remaining in the study and transferring to another site to complete study procedures. Subjects may have some study procedures performed at other DIAN-TU sites if the procedure cannot be performed at the host DIAN-TU site (e.g., due to equipment failure). These subjects would remain enrolled at their host DIAN-TU site.

#### **4.6 Expectations and Withdrawal of Sites**

Sites are expected to fulfill all study obligations. DIAN-TU sites that fail to fulfill study obligations may be terminated from the study. While a site is on probationary status or if a site is terminated, subjects at that site will be offered the option of transferring to a different DIAN-TU site on a temporary or, if the site is terminated, permanent basis. After obtaining signed release from subjects, copies of all source documents should be made available to the new site as rapidly as possible and at least within 30 days after probationary status begins.

### **5 STUDY DRUGS**

See each drug-specific appendix for drug-specific background, preclinical and clinical data, rationale for specific biomarkers endpoints to assess target engagement, risks/benefits and specifics of drug packaging, preparation, administration, compliance, analysis issues, and drug-specific adverse events, and schedule of visits.

The following information on blinding, concomitant medications, and treatment compliance applies to all drugs.

#### **5.1 Blinding**

Subjects and study staff will remain blinded as to whether subjects are on active drug or placebo. Subjects and staff will not be blinded as to the treatment route and interval. Although it is possible that study staff preparing parenterally administered compounds could be inadvertently unblinded, procedures are designed to reduce the risk of inadvertent unblinding and to ensure that study staff who might become unblinded (e.g., pharmacists) have minimal contact with other study staff and no direct contact with subjects and do not participate in other study assessments. Research staff that do home or remote visits may have one home health nurse prepare and administer study drug while the other home health nurse conducts the study procedures. The procedures taken to maintain blinding are detailed in each drug-specific appendix.

During double-blind periods, genetic status will not be disclosed to either the subject or study staff. Mutation positive subjects may already be aware of their genetic status and choose to

disclose this to study staff. The mutation positive subjects will be encouraged not to disclose their genetic status to study staff. For subjects who have not been provided with their mutation status, the staff will be encouraged not to make assumptions about genetic status or group assignment within a study drug arm when adverse events (AEs) are reported. Genetic status will be confirmed for entry into any OLE period.

## 5.2 Breaking the Blind

With the exception of the periodic DSMB data review or required regulatory reporting for expedited reports by designated safety personnel who do not have contact with study staff or subjects, the study blind will not be broken until all subjects in a blinded study drug arm have completed the double-blind treatment period and the database for that study drug arm is locked. Only in the case of an emergency, when knowledge of the study drug is essential for the immediate clinical management or welfare of a specific subject, may the investigator unblind a subject's treatment assignment.

Prior to any unblinding, the investigator is strongly advised to discuss options with the Medical Director or appropriate sponsor study personnel or designee. As soon as possible, and without revealing the subject's study drug assignment (unless important to the safety of subjects remaining in the study), the investigator must notify the sponsor if the blind is broken for any reason and the investigator was unable to contact the sponsor prior to unblinding. The investigator will record in source documentation the date and reason for revealing the blinded treatment assignment for that subject.

## 5.3 Concomitant Medications

All concomitant medication taken during the study must be recorded on the Concomitant Medication electronic case report form (eCRF). Subjects will be instructed to consult the investigator or other appropriate study personnel at the site before initiation of any new medications or supplements and before changing dose(s) of any current concomitant medications or supplements.

To approximate standard of care for AD, use of approved treatments for AD is permitted in this study, and no AD medications are explicitly excluded from use. This section provides additional guidance on managing concomitant medication use during the trial.

**Allowed Medications.** Use of approved treatments for AD (including donepezil [Aricept®], rivastigmine [Exelon®], galantamine [Razadyne®, Razadyne®ER], tacrine [Cognex®], and memantine [Namenda®]) is permitted during the study, provided that such medications have been given for at least 90 days and the dose has been unchanged for 2 months (60 days) before ██████████ Visit 2. Doses of these medications should remain constant throughout the study.

If a subject has recently stopped acetylcholinesterase inhibitors (AChEIs) and/or memantine, he or she must have discontinued treatment at least 90 days before [REDACTED] Visit 2. Other vitamins or nutraceuticals given for their possible effects on AD may be continued on stable doses beginning 90 days before [REDACTED] Visit 2.

Starting, stopping, or changing doses of AChEIs and/or memantine during the study could interfere with outcome measures and may therefore result in discontinuation of the subject from the study.

***Before a subject starts, stops, or changes doses of AChEIs and/or memantine or other treatments for their AD, the sponsor or designee should be contacted to determine whether or not the subject should continue in the study and whether or not clinical outcome measures should be performed. If documentation of sponsor discussion and approval in advance of starting, stopping, or changing doses is in place, this will not be considered a protocol deviation.***

***If changes are made without prior contact with the sponsor or designee, the principal investigator, once informed of these changes, should contact the sponsor or sponsor's designee to discuss and jointly determine whether or not the subject should continue in the study and whether or not clinical outcome measures should be performed. It will be considered as a protocol deviation if discussion and sponsor approval prior to the start, stop, or modification of such medications were not in place***

Non-medication treatments for AD such as psychotherapy are permitted but are subject to the same restrictions as medication treatment taken for AD.

Other concomitant medications that affect CNS function may be given if the dose remains unchanged throughout the study. Doses of these compounds should remain constant from 4 weeks before [REDACTED] before randomization (Visit 2).

To avoid effects on cognitive measures, subjects should not stop receiving any medications that affect CNS function during the study, add any to the treatment regimen, or change doses of these medications. If unforeseen starting, stopping, or changing of stable doses of these drugs occurs during the study, the Medical Director or designee must be contacted to determine whether or not the subject should continue in the study and whether or not outcome measures should be performed.

Use of benzodiazepines for treatment on an as-needed basis for insomnia or daily dosing as anxiolytics is permitted. Use of sedatives or hypnotics should be avoided for 8 hours before administration of the cognitive tests unless they are given chronically.

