6. Subject can no longer contribute to the collection of key outcomes data. Thus, a subject who cannot contribute to both the biomarker endpoint and cognitive endpoint during the first 2 years of the study or the cognitive endpoint after the first 2 years of the study should be discontinued from the double-blind treatment period but is eligible for continued clinical and/or cognitive follow-up and/or OLE\* (refer to section 6.3.7).
7. Known negative mutation carrier status. For example, if a subject enters the study unaware of their mutation status, but later learns that they are mutation negative, they would be discontinued from the study.

8. For subjects in the primary prevention population: if a subject enters the study based on their family pedigree, but later learns that the at-risk parent is a non-carrier, they would be discontinued from the study.
9. For subjects administered [F]AV-1451 tau PET tracer, the following additional discontinuation criteria apply:
  - a. Participants who exhibit hypersensitivity to [F]AV-1451 or any of its excipients are to be discontinued from this protocol addendum and are **not** to have another [F]AV-1451 dose administered.
  - b. Discontinuation or Holding of [F]AV-1451 dose for participants who take medications that prolong QT interval:
    - i. Participants who begin taking a medication known to prolong QT interval prior to the baseline [F]AV-1451 scan will be discontinued.
    - ii. Participants who begin taking a medication known to prolong QT interval after the baseline scan and continue to take medication at the time of the next scheduled [F]AV-1451 scan will be discontinued.
    - iii. If a participant receives a course of a QT prolonging medication and has stopped taking the medication prior to a scheduled [F]AV-1451 scan, the advisability of administering the next scheduled dose of [F]AV-1451 and performance of the [F]AV-1451 PET scan or holding the dose of [F]AV-1451 should be considered by the Site principal investigator in consultation with the Sponsor

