If a subject discontinues early from the double-blind treatment period, every effort will be made to complete all study assessments, as applicable, at an Early Termination visit. **These assessments would not be completed for subjects who are withdrawn because they become unblinded to genetic status and are found to be mutation negative.**

  
\*Any subject that discontinues from treatment due to safety reasons or inability to continue treatment and/or key study procedures will be encouraged to continue with any clinical or cognitive measures able to be performed based upon the assessment schedule. The assessments will be determined based on discussion with the site principal investigator and sponsor.

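### Section 5.3 permits avoidable, outcome-related truncation of DIAN-MCE data after a change in AD or other CNS medication

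*Protocol*

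**What the plan says.** Section 5.3 permits approved AD treatments, excludes none outright and asks that doses stay constant. It then warns: "Starting, stopping, or changing doses of AChEIs and/or memantine during the study could interfere with outcome measures and may therefore result in discontinuation". The sentence goes on to make clear that this means leaving the study, not only study drug.

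- **AD-drug change, sponsor contacted beforehand.** The sponsor or designee determines "whether or not the subject should continue in the study and whether or not clinical outcome measures should be performed". A change approved in advance is not counted as a deviation.
- **AD-drug change without prior contact.** The investigator and the sponsor or its designee are to "discuss and jointly determine whether or not the subject should continue in the study and whether or not clinical outcome measures should be performed".
- **Other CNS-active drugs.** The Medical Director or designee is contacted "to determine whether or not the subject should continue in the study and whether or not outcome measures should be performed". The qualifier *clinical* is absent here.

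The ground given is interference with outcome or cognitive measures. No criterion is set for either decision, and no duration for an omission. Section 5 gives the rule platform-wide scope: "The following information on blinding, concomitant medications, and treatment compliance applies to all drugs".

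**The concern.** The primary endpoint is repeated DIAN-MCE measurement over at least four years, and section 3.1 says the assessments beyond year 4 also count towards it. More than half of the carriers enter cognitively normal. For such a subject, starting a cholinesterase inhibitor or memantine is a plausible response to emerging symptoms, which is the change the DIAN-MCE is meant to measure. Section 5.3 makes that event an occasion to end participation or skip measurements. Missing data would then be tied to the outcome by a rule of the protocol.

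This is a data-collection matter. An analysis plan can decide how to treat scores obtained after a medication change, but only if they were obtained.

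**Working it through.** **1. The plan's nearest figure.** The synopsis allows for 5% annual attrition over four years: 52 × 0.95⁴ = 42.35 and 34 × 0.95⁴ = 27.69, against the stated 42 and 27. The figure reproduces and is not disputed. It is a general allowance and does not say how many losses 5.3 might cause.

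**2. Which components 5.3 reaches.** Section 3.6 lists the MMSE under clinical measures, with the CDR, GDS, NPI-Q and FAS. The shopping list, Digit Symbol and Logical Memory tests sit in the cognitive battery.

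- AD-drug change, measures omitted: the MMSE for certain; the other three only if *clinical outcome measures* is read broadly.
- Other CNS-drug change, measures omitted: all four.
- Participation ended after either change: all four.

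**3. Whether another section overrides 5.3.**

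- Section 4.4.1 does not list a medication change as its own criterion. Item 2 is general enough to cover one: "Site principal investigator, Medical Director, PAL, or Medical Monitor decides subject should be discontinued".
- Item 6 concerns subjects who can no longer contribute key outcome data. Such a subject "should be discontinued from the double-blind treatment period but is eligible for continued clinical and/or cognitive follow-up".
- On early discontinuation, "every effort will be made to complete all study assessments, as applicable, at an Early Termination visit". Section 6.3.7 lets the sponsor drop early termination procedures case by case.
- Section 6.3.7 encourages continued assessments but does not require them, and the choice of assessments is made with the investigator and sponsor. The starred note in 4.4.1 covers only safety reasons or inability to continue.
- These clauses attach to stopping treatment or leaving the study. None addresses a subject who stays on treatment while measures are omitted under 5.3.

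**4. Conditional count to week 208.** Section 6.1.14 schedules post-baseline cognitive testing at weeks 24, 52, 76, 104, 128, 156, 180 and 208, which is 8 visits. The MMSE is given at the annual visits (52, 104, 156, 208), which is 4. The last column credits one early termination visit with the full Visit 54 procedures (Appendix 3, 3.3.16; Appendix 4, 3.3.17).

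| Assumed event | Cognitive visits lost | MMSE lost | Net of early termination visit |
|---|---|---|---|
| MMSE alone omitted at one annual visit | 0 of 8 | 1 of 4 | not applicable |
| All measures omitted at one annual visit | 1 of 8 | 1 of 4 | not applicable |
| Testing stops after week 52 | 6 of 8 | 3 of 4 | 5 of 8; 2 of 4 |
| Testing stops after week 104 | 4 of 8 | 2 of 4 | 3 of 8; 1 of 4 |
| Testing stops after week 156 | 2 of 8 | 1 of 4 | 1 of 8; 0 of 4 |

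The early termination visit falls at exit, so the time from exit to week 208 stays unobserved. The protocol gives no rate of medication change or removal, so no expected number of subjects follows.

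**5. Direction.** An illustrative simulation used assumed inputs: normal slopes with placebo mean 1 and SD 1 or 0.7, true slowing of 40%, a medication change in subjects declining faster than the placebo 70th percentile, and 25% to 100% of those losing their data. Loss was 7.5% to 30% on placebo and about 3% to 18% on active. Apparent slowing ranged from about 35% to 44%, above 40% with SD 1 and at or below it with SD 0.7. The absolute slope difference shrank by about 6% to 45%. With no true effect, loss was equal and no bias appeared. These are naive means, not the planned disease progression model, which would use data collected before the loss. They show only that the direction depends on inputs the protocol does not give.

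**The case against.** The strongest reply is that 5.3 foresees subjects changing AD drugs and remaining in the trial. Removal is discretionary, advance approval is available, and the decisions are made in a blinded trial. The reason for the rule, keeping symptomatic-drug effects out of the scores, is an understandable choice. Section 6.3.7 bases continued assessment on the subject's capabilities, the benefit to the study and the risk, and participation is voluntary, so encouragement is about as far as wording can go for someone who wants to leave. All of this stands, and it limits the point to what the rule permits.

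It does not remove the point. A subject willing to be tested can still go untested by decision, without criteria.

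Three stronger readings may tempt a reader, and the documents do not support them.

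- *All four tests may be withheld after an AD-drug change.* The clause says clinical outcome measures, and only the MMSE is certainly among them.
- *The rule biases active against placebo, in a known direction.* Nothing in the protocol fixes this.
- *Affected subjects drop out of the primary analysis.* Under section 8.4.1 one post-baseline assessment of the primary cognitive outcomes is enough for mITT, so records are cut short rather than removed.

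**Conclusion.** The point holds as a fault in a data-collection rule. Section 5.3 allows participation to end after an AD-drug or other CNS-drug change. It also allows omission of at least the annual MMSE in the first case and of any outcome measure in the second. Since such changes can follow decline, it permits outcome-related truncation of primary data that could be avoided. Sections 4.4.1 and 6.3.7 soften this without overriding it.

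The conclusion rests on one clinical assumption: that changes in AD or CNS medication are sometimes prompted by cognitive worsening. The fractions in the table are conditional on assumed events and do not measure risk. Section 6.3.5 has double-blind visits in the gantenerumab and solanezumab arms ending by November 2019, so the practical value lies mainly with arms added later, to which section 5 extends the rule.

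**What to change.** Replace the discretionary wording in 5.3 with text such as: *The change and its date are recorded. A change in AD or CNS medication is not by itself a reason to end study participation or to omit scheduled clinical or cognitive assessments. A test may be deferred briefly within its visit window for an acute medication effect. Decisions on study drug for safety are unchanged.* Leave the handling of post-change scores to the SAP, with a sensitivity analysis.

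The cost is protocol wording, plus consent wording if it repeats the rule; the visits are already scheduled. The downside is that some scores will carry a symptomatic-drug effect. With the date recorded, that effect can be examined in analysis, whereas scores never taken cannot.
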